- The MRI scanner produces a loud hammering noise, which has produced hearing loss in a very small number of patients. You will be given earplugs to reduce this risk, and headphones for added protection.
- If you are a woman of childbearing potential, there may be unknown risks to the fetus. Therefore, before you can have the MRI, you must have a pregnancy test.
- If an obvious abnormality is discovered during your MRI scan, you will be informed about it by the research team, you will be provided with a copy of your MRI scan and we will encourage you to see your primary care physician. MRI will only be done for research purposes in this study.
- You will be monitored very carefully while in the scanner, and repeatedly checked to ensure comfort.

There is a risk of introducing metal into an MRI environment. However, the MRI compatible transcranial direct current stimulator contains no materials that respond to the MRI environment. Thus, the risks associated with undergoing MRI while receiving stimulation are the same as transcranial electrical stimulation outside the MRI scanner.

Transcranial direct current stimulation. Transcranial direct current stimulation is considered safe but a small number of people do experience some side effects. The most common side effects are itching and tingling or mild discomfort at the area of stimulation, and headache. Other possible side effects include dizziness and nausea. Whenever an electrical stimulation is applied to the body, it could possibly cause a seizure or abnormal heartbeat, but this has never occurred with the transcranial direct current stimulation parameters used in this study.

Although there is no known risk to pregnancy, there may be unknown risks and all women of child bearing potential must have a negative pregnancy test prior to stimulation.

Cognitive Training. There is a risk participants will find cognitive training on the computer challenging, fatiguing, and/or boring. Research staff will explain what to do and how to perform the training tasks tests during your initial study visit. Participants will also have access to a 24-hour help line should you have trouble working with the training computer.

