Monitoring mental health and safety. At each assessment visit, participants will complete the BDI to assess for depressive symptom severity. Any participant who endorses clinical levels of any psychiatric disorder or who endorses suicidality will be referred to [name], study psychologist, for further follow-up assessment. The psychologist will then provide a recommendation regarding the appropriate course of follow-up and also advise on whether it is safe for the participant to continue in the study. If a participant is found to be actively suicidal with a plan and/or intent, they will be escorted immediately to the emergency room at the Shands Hospital at the University of Florida. If safety is an issue, UF security or local authorities will be called for assistance. If a participant endorses suicidal thoughts or significant psychopathology, participants will be referred for further evaluation with [name] (Licensed psychologist and co-investigator). Based on this evaluation, she will recommend follow-up assessment and treatment appropriate to the situation including treatment at the Psychology and/or Psychiatry Clinics within Shands Hospital at the University of Florida.

Adverse Event Reporting. An **adverse event (AE)** is defined as any unfavorable and unintended sign (including an abnormal laboratory finding), symptom, or disease temporally associated with the intervention irrespective of whether it is considered related to the intervention.

Non serious adverse events. Defined as conditions that may be unpleasant and bothersome to the participant that does not require discontinuing the study.

Serious adverse events (SAEs). Defined as events that may be harmful to the participant and/or may be serious enough to warrant either temporary or permanent discontinuation of the study intervention, either because they are intolerable or because they are judged to be potentially harmful. All serious adverse events require immediate reporting and an assessment of the implications for the continuation of the study and/or modification of the consent form. The following are considered serious events:

- It is acute or life threatening;
- It results in prolonged, permanent or severe disability;
- It is another severe illness including worsening of a pre-existing condition, injury or accidents;
- It is an inpatient hospitalization or surgical procedure, or a treatment to prevent a serious event;
- It results in death;

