- It is a clinically significant abnormal laboratory or diagnostic test.

Table 3. Adverse Event (AE) Classification

Adverse Event (AE) Classification	
Definite.	Temporal pattern + known or expected AE response pattern + confirmed by stopping the intervention + reappearance of AE on re-challenge
Probable.	Temporal pattern + known or expected AE response pattern + confirmed by stopping the intervention + could not be explained by participant's clinical state
Possible.	Temporal pattern + known or expected AE response pattern + could have been produced by a number of other factors
Unknown.	Relationship for which no evaluation can be made
Not related.	AE for which sufficient information exists to indicate that the cause is unrelated to the study intervention

Classification of AE severity. The principal investigator will

evaluate adverse events for seriousness, expectedness, severity, and relationship to study intervention at each study visit. The primary mechanism for ensuring participant safety will be clinical observation of symptoms. The study will be conducted and supervised by trained study staff that are certified in CPR and will monitor potential adverse experiences and symptoms. During each visit, participants will log any health-related problems or symptoms they are experiencing. These sheets will be reviewed by study staff before allowing the participant to continue. Community health services will be contacted immediately if warranted by the participants' symptoms.

All adverse events (AEs) will also be categorized according to the likelihood that they are related to the study intervention. Specifically, they will be labeled either definitely, probably, possibly or unrelated to the study intervention. The classification of potential relationship to the intervention is shown in Table 3.

Effective screening will exclude individuals who would be at increased medical risk as a result of participation in this research. FMRI contraindications, such as claustrophobia or some metal implants will be assessed by telephone screening and again on the day of the scan. [name], who has completed MRI safety training and Protocol IRB #201400328

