has over 4 years experience screening FMRI participants, will supervise these procedures. The RA who will conduct neuroimaging analyses will be trained in UF AMRIS safety procedures and will also be responsible insuring for participant safety. Adverse events, although unlikely, may occur as a result of neuroimaging.. Such events will immediately be reported by [name] (PI) to the local IRB, with serious adverse events reported to both the IRB and NIH.

SAE reporting. Serious adverse events (SAEs) that are unanticipated, serious, and possibly related to the study intervention will be reported within 24 hours of study's knowledge of the SAE to the Independent Monitor, IRB, and CTSA in accordance with the regulatory requirements. Anticipated SAEs or those unrelated to the study intervention will be reported to the same individuals/entities in accordance with regulatory requirements.

Minor events will be reported to the IRB at the time of annual review, as well as to the oversight committee on a bi-annual basis. Both the principal investigator and the study staff will review the study weekly and examine reports of adverse incidents and reports of study participant recruitment and follow-up. Throughout the course of the study, information regarding issues deemed critical to the study or to the safety of research participants will be provided to the principal investigator and other study investigators as needed. As a result of receiving this critical information, a meeting to discuss this information may be convened. Information deemed critical would include:

- serious and non-serious adverse events that may occur;
- suspicion of scientific fraud or misconduct;
- any other issues which may warrant protocol changes or modifications.

Adverse event (AE) and serious adverse event (SAE) determination and monitoring will be achieved via administration of structured questionnaires. Standardized forms for referring and treating study participants who experience adverse events will be in place.

Documentation of Training on Protection of Human Participants. All key personnel on the study have successfully completed and obtained certification from their respective institutions for Mandatory Education in Human Research Subjects Protection. The Mandatory Education is described as follows:

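### Table 3 builds expectedness into causality, so a serious event of a wholly new type may have no related category and may miss the 24-hour report

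*Combined protocol and SAP*

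**What the plan says.** All of this is in section 7 of the protocol, from Adverse Event Reporting to SAE reporting.

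- **Table 3, Definite:** "Temporal pattern + known or expected AE response pattern + confirmed by stopping the intervention + reappearance of AE on re-challenge".
- **Table 3, Probable:** after the temporal pattern, "known or expected AE response pattern + confirmed by stopping the intervention + could not be explained by" the participant's clinical state.
- **Table 3, Possible:** "Temporal pattern + known or expected AE response pattern + could have been produced by a number of other factors".
- **Table 3, Unknown:** "Relationship for which no evaluation can be made".
- **Table 3, Not related:** reserved for events where there is enough information to point to a cause other than the intervention.
- **Classification of AE severity:** the principal investigator rates four things, among them expectedness and relationship, as separate items. On relationship, the text says of adverse events that "they will be labeled either definitely, probably, possibly or unrelated to the study intervention", and then refers to Table 3.
- **SAE reporting:** "Serious adverse events (SAEs) that are unanticipated, serious, and possibly related to the study intervention will be reported within 24 hours". The recipients are the Independent Monitor, the IRB and the CTSA. SAEs that were anticipated, or that are unrelated, go to the same recipients as regulation requires, with no clock stated.
- **Serious adverse events (SAEs):** "All serious adverse events require immediate reporting and an assessment of the implications for the continuation of the study". No recipient or time limit is given there.

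**The concern.** Causality and expectedness answer different questions. Causality asks whether the intervention could have produced the event. Expectedness asks whether the event was foreseen. The plan intends to keep them apart, since it lists them as separate ratings. Table 3 nevertheless makes a recognised pattern a condition for calling an event related at any level. An expedited rule that asks for unanticipated and related events then depends on a table that makes relatedness hard to assign to the least foreseen events.

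What is at stake is prompt independent notice of a new kind of serious harm. The Data and Safety Monitoring Plan says that there will be no external data and safety monitoring board. The Independent Monitoring Committee reviews twice a year, and the principal investigator makes the relatedness call. The 24-hour report is the only route to an independent monitor with a short stated clock, so a gap in it for novel events matters more here than in a trial with an external board.

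**Working it through.** No figure is involved and there is none to reproduce. The check is logical: set the Table 3 categories beside the labels in the text and the reporting rule. I take possibly related in the 24-hour rule to mean Possible or higher.

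| Table 3 category | Recognised pattern required? | Among the labels in the text? | Route if the SAE is unanticipated |
|---|---|---|---|
| Definite | Yes | Yes | 24 hours |
| Probable | Yes | Yes | 24 hours |
| Possible | Yes | Yes | 24 hours |
| Unknown | No | No | Not stated |
| Not related | No | Yes | Same recipients, no clock stated |

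Step 1. The elements of each related category are joined by plus signs, so each element is required. The pattern condition is in 3 of 3 related categories and in 0 of the other 2.

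Step 2. Take a serious event of a wholly new type that follows stimulation closely in time. It meets the temporal element and fails the pattern element. It cannot be Possible, the least demanding of the three, and so cannot be Probable or Definite.

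Step 3. It does not belong in Not related either, because that category needs positive information pointing to another cause. What remains is Unknown.

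Step 4. Table 3 has 5 categories and the text gives 4 labels; the one left out is Unknown. The SAE reporting paragraph has one sentence for unanticipated, possibly related SAEs and one for SAEs that are anticipated or unrelated. An unanticipated SAE of Unknown relationship fits neither, so its route is not stated.

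Step 5. Test whether the 24-hour rule can be met at all. This turns on how the pattern condition is read.

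- *Reading A: a known or expected pattern means the same as an anticipated event.* Then none of the 3 related categories can hold an unanticipated event, and the rule is empty.
- *Reading B: the pattern is a criterion for judging causality, and expectedness is a separate rating.* Then all 3 related categories can hold an unanticipated SAE, for example a known type of event at a severity nobody anticipated.

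The documents do not define unanticipated and do not equate the two terms. Table 3 offers known as an alternative to expected, and the text lists expectedness separately, which favours Reading B. The event in Step 2 has no related category under either reading, because it has no recognised pattern in any sense.

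Step 6. Compare the two reporting sentences. One asks for immediate reporting of every SAE, without condition, recipient or time limit. The other names the recipients and a clock but applies the clock to a subset. The same SAE is therefore subject to two rules that the protocol does not reconcile.

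**The case against.** A reader might infer that the 24-hour rule can never be triggered, because no event can be both unanticipated and related. The documents do not support that. It needs Reading A, which they nowhere state. They also name effects that are recognised but not observed: of stimulation, the risk section says that "it could possibly cause a seizure or abnormal heartbeat, but this has never occurred with the transcranial direct current stimulation parameters used in this study". A rater could treat such an event as fitting a known pattern and still call it unanticipated, and the rule would then apply. For the same reason a seizure is a poor illustration of the gap; the clean case is an event of a kind that the protocol does not foresee at all.

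A reader might also infer that novel events will be pushed into the unrelated group, so that a clean safety summary is guaranteed. Table 3 does not say so: Not related needs evidence of another cause. The four-label sentence may be no more than a loose summary of a table that it points to. The plan also commits to no particular safety conclusion; the Safety Review Plan describes a list and summary of adverse events and a check of rates against pre-study assumptions.

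The strongest defence is that serious events are caught elsewhere. Every SAE is to be reported immediately, the Data and Safety Monitoring Plan has all reported events forwarded to the IRB, and the principal investigator and staff review the study weekly. This stands in part. A novel SAE is not screened out of reporting. But the immediate-reporting sentence names no recipient or deadline, the forwarding sentence gives no deadline, and the weekly review is internal. None of them guarantees the Independent Monitor notice within 24 hours. The immediate reporting of neuroimaging events does not help either, since it covers events arising from imaging.

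**Conclusion.** The point holds in a limited form. On the literal wording of Table 3, a serious event with no known or expected pattern cannot be rated Possible or higher. It falls to a category that the text omits and the SAE reporting paragraph does not route, so it may miss the 24-hour report. This rests on reading the plus signs as joint requirements and possibly related as Possible or higher.

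The gap is confined to events of a wholly new type. It does not make the expedited rule empty, and the general sentence on immediate reporting is a partial backstop. The documents give no basis for estimating how often such an event would occur among the 90 participants, so no rate can be attached. It is a wording defect of moderate weight. It deserves correction mainly because there is no external board and the 24-hour report is the one short-clock route to an independent monitor.

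**What to change.** 1. In Table 3, remove the known-or-expected pattern as a required element of Possible. In Probable and Definite, make it supporting evidence, not a condition. Expectedness is then judged only in its own rating, as the text already intends.
2. Use the same five categories in the text below Table 3 as in the table, including Unknown.
3. State in SAE reporting how an unanticipated SAE of Unknown relationship is handled, for example through the same 24-hour report.
4. Reconcile the sentence on immediate reporting of all SAEs with the SAE reporting paragraph, so that there is one timeline with named recipients.

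This changes one table and a few sentences and leaves design and sample size as they are. The cost is that a few more events would be reported within 24 hours.
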